#### **8.2.2. Analysis methods**

The primary endpoint is the time to colorectal cancer screening. The date of the pre-intervention survey will be considered Day 0. The date of screening will be considered the date of the event. The date of follow-up phone call will be considered the date of event for subjects for whom a screening result is not recorded in the medical record and who self-report that screening was done. We will conduct a Cox proportional hazards regression model with study arm to evaluate our primary endpoint. In the per-protocol population, we will conduct similar analyses and include age group and gender as independent variables.

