### **3. TRIAL DESIGN**

This is a two-arm, open-label, randomized controlled study. Men and women between 50-75 years of age who have never undergone a screening test for colorectal cancer (and who have no known history of Ulcerative Colitis, Crohn's disease, Familial Adenomatous Polyposis, Lynch Syndrome, Personal history of colon cancer) will be randomized to the colorectal cancer risk information arm (CRCRAT arm) or to the no risk information arm (control arm). The study period for subjects will end approximately 12 months post-randomization.

Stanford Primary Care Clinic subjects who meet eligibility criteria will be identified through a pre-existing outreach list. A brief chart review will be conducted to ensure subjects meet particular inclusion/exclusion criteria. A letter will be sent to eligible subjects (along with the HIPAA authorization form), describing the research study and informing subjects that they will be contacted in the near future. Subjects will be provided with the option to "opt-out" of being contacted. Subjects will be contacted a few weeks later to give all subjects adequate time to respond.

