Eligible subjects will be contacted using an approved telephone script to provide verbal consent for participation in the study. If a subject agrees to participate in the study, they will be immediately randomized, using blocked randomization, to either the CRCRAT or control arm. Both groups will then undergo a pre-intervention survey designed to assess attitudes towards colorectal cancer screening. Study interventions will be administered during this same telephone encounter. The control and intervention arms will both be read general information about colorectal cancer. The CRCRAT arm will then be guided through a series of questions from the NCI Colorectal Cancer Risk Assessment Tool in order to calculate their personalized risk of colorectal cancer. This personalized risk score will be recorded and subjects will be provided with the information on their risk scores. Immediately following these interventions, both arms will undergo a post-intervention survey, which again assesses attitudes towards colorectal cancer screening. Over the next 6 and 12 months, subjects' electronic medical records will be reviewed for colorectal cancer screening status. Subjects who were not screened, per their electronic medical record, will be contacted via phone or mail to see if they were screened elsewhere and/or assess their current screening intent. Subjects will be contacted no more than 3 total times for this research study.

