#### **3.1 Statistical hypothesis for trial objectives**

**The primary endpoint is time to colorectal cancer screening by end of follow up at 12 months.** This will be determined by a review of subjects' electronic medical records and patient self-report. Subjects for whom a screening result is not recorded in the

EMRs will be classified based on patient self-report of screening. The hypothesis to be tested is that an intervention which provides subjects with their colorectal cancer risk information, compared to not providing this information, increases colorectal cancer screening rates based on the primary endpoint.

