### **8.2. Primary Efficacy Endpoint**

#### **8.2.1. Definition**

The primary endpoint is time to colorectal cancer screening by end of follow up at 12 months. This will be determined by a review of subjects' electronic medical records. Subjects for whom a screening result is not recorded in the EMRs will be deemed to have not had colorectal cancer screening.

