## 8.3. Secondary endpoints

### 8.3.1. Definitions

#### 1) Colorectal cancer screening rates at 12 months

The secondary endpoint is whether a subject has had colorectal cancer screening at 12 months. Each subject will have an indicator of “Yes” or “No” for whether they were screened for colorectal cancer at 12 months. This will be determined by a review of subjects’ electronic medical records at 12 months post-randomization. Patient self-report on screening will be used for subjects for whom a screening result is not recorded in the EMR.

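### Screenings known only by self-report are dated to the follow-up call in the primary Cox model, with no contact window or censoring date

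*Combined protocol and SAP*

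**What the plan says.** **Dating.** In section 8.2.2 the clock starts at the baseline call: "The date of the pre-intervention survey will be considered Day 0". For screenings in the record, "The date of screening will be considered the date of the event". For the others, "The date of follow-up phone call will be considered the date of event for subjects for whom a screening result is not recorded" in the chart and who say they were screened.

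**Contacts.** Section 3 (Trial Design) has records reviewed at 6 and 12 months, after which "Subjects who were not screened, per their electronic medical record, will be contacted via phone or mail to see if they were screened elsewhere". The dating rule mentions only a phone call; nothing dates a mail reply.

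**End of follow-up.** Section 8.2.1 runs the endpoint to the end of follow-up at 12 months. Section 3 says "The study period for subjects will end approximately 12 months post-randomization". No section gives a contact window, a censoring date, or a rule for an event dated after month 12. Section 8.1.2 says only that partial data will be included.

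**Whether self-report counts.** Section 3.1 says subjects with no result in the "EMRs will be classified based on patient self-report of screening". Section 8.2.2 agrees, since it assigns those subjects an event date. For the Yes/No endpoints, section 8.3.1 says "Patient self-report on screening will be used for subjects for whom a screening result is not recorded in the EMR". Section 8.2.1 says the opposite for the primary endpoint: "Subjects for whom a screening result is not recorded in the EMRs will be deemed to have not had colorectal cancer screening".

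**The concern.** A call that asks whether screening has happened cannot come before the screening. Each self-reported event is therefore dated on or after its true time. A screening elsewhere in month 2 is dated to about month 6 or later, and one in months 6 to 12 to about month 12 or later. What is actually known is an interval, but the Cox model takes the call date as exact. Part of the primary event times then reflects the contact schedule.

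The open end of follow-up adds to this. If follow-up is cut at exactly 12 months, an event dated to a later call is lost from the Cox analysis, although the 12-month Yes/No endpoint counts the same subject as screened. If follow-up runs to the call, the event is kept. The plan does not choose, so the primary result could depend on a decision made at analysis.

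All of this applies only if self-report counts, and section 8.2.1 says it does not.

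**Working it through.** **1. Reproduce the plan's sample size (section 3.2).** Inputs: 50% screened by 6 months in control, 65% in the CRCRAT arm, 1:1 allocation, two-sided 0.05. Power is not stated; 80% is inferred.

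- HR = ln 0.35 / ln 0.50 = 1.515.
- Schoenfeld events = 4(1.960 + 0.842)² / (ln 1.515)², about 183.
- 12-month screening probability under exponential times: control 1 − 0.50² = 0.75; CRCRAT 1 − 0.35² = 0.8775; mean 0.814.
- N = 183 / 0.814 = 225, the plan's figure.

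**2. Events affected.** Take 112 control and 113 CRCRAT subjects, and let q be the share of screenings known only by self-report. The documents do not give q; 10, 20 and 30% are assumed, equal in both arms.

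- All screenings by month 12: 0.75 × 112 + 0.8775 × 113 = 183.
- Months 0–6, dated to the 6-month call: q × (0.50 × 112 + 0.65 × 113) = 12.9 / 25.9 / 38.8.
- Months 6–12, dated to the 12-month call: q × (0.25 × 112 + 0.2275 × 113) = 5.4 / 10.7 / 16.1.

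If calls fall 0–1 month after each review, some screenings just after month 6 are caught at the 6-month call. The number truly screened by month 12 but dated after it is then about 5 / 9 / 14.

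**3. Size of the delay.** With the same call window, the simulated mean delay of affected events is 3.7 months.

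**4. Effect on the primary test, equal shares.** Simulation with N = 225, exponential times, control hazard ln 2 / 6 per month, HR 1.515, no dropout, everyone reached, calls 0–1 month after months 6 and 12, and a Cox Wald test. There were 20,000 trials, with the same event times in every scenario (standard error about 0.3 points).

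| Handling | HR at q = 10 / 20 / 30% | Power at q = 10 / 20 / 30% |
|---|---|---|
| True dates | 1.515 | 79.6% |
| Call date, cut at 12 months | 1.499 / 1.487 / 1.477 | 76.7 / 73.6 / 71.1% |
| Call date, follow-up run to the call | 1.504 / 1.492 / 1.481 | 78.8 / 77.0 / 75.3% |
| Interval midpoint | 1.513 / 1.510 / 1.507 | 79.4 / 78.9 / 78.7% |
| Self-report ignored (section 8.2.1) | 1.425 / 1.365 / 1.322 | 62.1 / 46.5 / 34.2% |

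Widening the call window to 0–2 months at q = 20% gives 73.9% (cut) and 77.4% (run to the call).

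A third reading keeps the late events but censors everyone else at 12 months. It gives power of 77 / 74 / 67% in 1,500 trials and 76 / 73 / 69% in 4,000.

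**5. Unequal shares.** These are also assumed (1,500 trials per setting, error about 1 point on power). Ranges cover the 12-month cut and the third reading.

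| Share CRCRAT / control | HR and power, true HR 1.515 | HR and rejection rate, true HR 1 |
|---|---|---|
| 20% / 10% | 1.37–1.39, 56–58% | 0.93, 7–8% |
| 10% / 20% | 1.60–1.62, 89% | 1.07, 6–7% |
| 30% / 10% | 1.27–1.29, about 36% | 0.87–0.88, 13–14% |

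Midpoint dating brings the true-HR-1 cases back to HR 0.99–1.00 with rejection of about 5%.

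**The case against.** The rule is pre-specified and identical in both arms, and dating an event to when it is ascertained is a common convention. With equal shares it costs power but creates no false positives: at a true HR of 1 and a 20 or 30% share, simulation gives HR 1.00 and rejection of 4.4–5.2%. At a 5% share, power is 78–80% against 81% with true dates in the same runs. Nothing in the documents supports a share as high as 30%, or different shares by arm.

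The plan can also be read as ending follow-up at the 12-month contact, since section 8.2.2 makes the call date an event date and section 3 ends the study only approximately at 12 months. That is the milder case in the table. The largest losses come from section 8.2.1, where the dating rule plays no part. Finally, a midpoint could count a screening done after month 12 but before the call, at about month 9.5.

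Most of this stands as a limit on size. The equal-share effect is modest, the share is unknown, and the section 8.2.1 figures are not evidence against the dating rule. Two parts do not carry the day. The milder reading is plausible but not written, and the competing reading follows from the 12-month limit in section 8.2.1. The absence of false positives also depends on equal shares, which an open-label trial does not guarantee. The midpoint edge case came to less than one event in simulation.

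**Conclusion.** The concern holds. Self-reported screenings are dated late, and the plan has no contact window, no censoring date and no date for mail replies. With equal self-report shares of 10–30%, the HR moves from 1.515 to about 1.48–1.50. Power drops by about 3 to 8 points if follow-up is cut at 12 months, and by about 1 to 4 points if it runs to the call. With unequal shares the estimate can be pushed either way and the type I error can exceed 5%.

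These sizes rest on an assumed share, an assumed 0–1 month call window, exponential times, no dropout and everyone reached. The direction of the dating error and the missing rules rest on the text alone. The conflict between section 8.2.1 and sections 3.1 and 8.2.2 has the larger effect (power 62 / 46 / 34% if self-report is ignored) and must be settled first. This should be corrected before analysis; it does not invalidate the design.

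**What to change.** 1. Reconcile sections 3.1, 8.2.1 and 8.2.2 on whether self-report counts in the primary endpoint.
2. If it counts, ask the month and year of the screening at each contact, by phone or mail, and use that as the event date.
3. If the date is not recalled, use the midpoint between the last date known unscreened (baseline or the earlier contact) and the current contact, capped at 12 months.
4. Count screenings done on or before 12 months. Censor all others at 12 months, or at last follow-up if earlier. State the contact window.
5. Add an interval-censored model, or a discrete-time model with intervals 0–6 and 6–12 months, as a sensitivity analysis.

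The cost is one added question at contacts already planned and a few lines in the SAP. If contacts are already complete, items 1, 3, 4 and 5 need no new data. The downside is some recall error in the reported month, and the midpoint is only a convention; the interval-based sensitivity analysis is there to test both.

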## 1. BACKGROUND

Colorectal cancer (CRC) is the third most commonly diagnosed cancer among men and women in the United States and the third leading cause of cancer death. Although CRC carries significant morbidity and mortality, the 5-year survival is 90% when detected at a localized stage. Unfortunately, given that CRC screening is still underutilized, less than half of colorectal cancers are diagnosed at this localized stage. According to the data from the National Health Interview Survey (NHIS), only 58.3% of U.S. men and women aged 50-75 have undergone CRC screening using one of the following approved methods: colonoscopy, sigmoidoscopy, fecal occult blood testing (FOBT), fecal immunochemical test (FIT), double contrast enema, CT colonography, and stool DNA test. Numerous factors have been associated with suboptimal screening rates. These factors can be categorized into a non-modifiable factors (age, ethnicity, gender, educational level, health insurance, socioeconomic status) and modifiable factors (knowledge about CRC and screening, attitudes toward screening, and perception of risk for developing CRC). Modifiable factors are of particular interest given their susceptibility to change. More specifically, risk perception, or perceived susceptibility, as defined by the Health Belief Model, refers to an individual's subjective assessment of risk of developing a given health problem. Studies have shown that high-risk perception of developing CRC correlates with higher screening uptake. Similarly, underestimation of personal CRC risk is associated with lower screening uptake.

The National Cancer Institute (NCI) Colorectal Cancer Risk Assessment Tool (CRCRAT) is a validated online tool available to the general public, which estimates an individual's short-term and lifetime risk of developing colorectal cancer. The goal of this study is to determine if providing subjects with their personalized colorectal cancer risk will influence colorectal cancer screening behavior and intent. If the study leads to an increase in colorectal cancer screening rates in the group of subjects receiving this information as compared to a group that does not receive this information, then the investigators will propose that primary care clinics consider adopting the Colorectal Cancer Risk Assessment Tool into their practice in order to encourage colorectal cancer screening and prevention.

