### **3.3 Randomization and blinding**

Subjects will be randomized 1:1 using block randomization stratified by gender (male/female) and age group (under 60 years old or 60 years old and over) to either the CRCRAT arm or control arm. The randomization scheme will be generated using the 'blockrand' package in R. The 'blockrand' function randomizes subjects to specified groups within sequential blocks; block sizes were randomly chosen from the set of 2, 4, 6, 8. The randomization scheme will be incorporated into REDCap in order to assign participants into the treatment groups. This is an open-label study with no blinding.

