## **8. EFFICACY ANALYSIS**

Our primary efficacy analysis will be performed on the intent-to-treat population. We will also conduct efficacy analysis on the per-protocol population.

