### 8.3.2. Analysis methods

To evaluate the secondary endpoint of colorectal cancer screening rates at 12 months and 6 months, we will conduct a logistic regression model in the ITT population,

separately for each time point, with study arm as the independent variable. In addition, we will include age group and gender as independent variables when conducting analyses in the per-protocol population

We will also calculate the proportion of subjects who were screened by study arm at 12 months and 6 months, respectively. For the CRCRAT arm, the numerator will be the total number of subjects who were screened and the denominator will be the total number of subjects randomized to the CRCRAT arm. For the control arm, the numerator will be the total number of subjects who were screened and the denominator will be the total number of subjects randomized to the control arm.

To evaluate the secondary endpoint of change in screening intent at post-intervention, we will use generalized linear mixed models, specifically multinomial logit random effects models, which include study arm and account for time (pre-intervention/post-intervention) and with a random effect for subject.

In the per-protocol population, we will conduct similar analyses and include age group and gender as independent variables.

In addition, we will explore how knowledge, fear, or perception of absolute or relative colorectal cancer risk affect screening intent. We will run separate models to evaluate the impact of these variables by adding each of them to the primary model explained above to determine if there is a change in the outcome. The definitions for each of these variables are based on responses to survey questions and details are provided in Table 2.

Table 2. Definitions for knowledge, fear and perception of colorectal cancer risk

Variable	Coding
Knowledge: Answered "Yes" to "Have you heard of at least one of the following colorectal cancer screening test?" (FOBT, FIT, Stool DNA test, Sigmoidoscopy, Colonoscopy, Double Contrast Barium Enema, CT Colonography, Did not provide answer/not answered)	If nothing is selected, then knowledge = 0 If heard of 1 test, then knowledge = 1 If heard of 2 tests, then knowledge = 2 If heard of 3 or more tests, then knowledge = 3 Did not answer=missing

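### Randomisation is stratified by gender and age group, but the ITT Cox and logistic models leave both factors out

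*Combined protocol and SAP*

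**What the plan says.** Section 3.3 describes 1:1 allocation by "block randomization stratified by gender (male/female) and age group (under 60 years old or 60 years old and over", which makes four strata. Section 8 fixes the population for the main analysis: "Our primary efficacy analysis will be performed on the intent-to-treat population".

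Section 8.2.2 then specifies the primary model: "We will conduct a Cox proportional hazards regression model with study arm to evaluate our primary endpoint". The next sentence brings in the stratification factors, but only for the other analysis set: "In the per-protocol population, we will conduct similar analyses and include age group and gender as independent variables".

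Section 8.3.2 repeats the pattern for the 6- and 12-month screening rates. The ITT logistic models are fitted "separately for each time point, with study arm as the independent variable", and then "we will include age group and gender as independent variables when conducting analyses in the per-protocol population".

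No section adds the factors to an ITT model, stratifies an ITT Cox model, or explains why the two analysis sets are modelled differently. Section 1 names age and gender among the "non-modifiable factors (age, ethnicity, gender, educational level, health insurance, socioeconomic status") that it links to poor screening uptake, without effect sizes.

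**The concern.** Stratified randomisation balances the arms on gender and age group. If those factors predict screening, the arm-only comparison varies less from trial to trial than its model-based standard error implies. The test is then conservative, and power is given up that two extra model terms would recover. This affects the primary test and two secondary tests.

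The arm-only hazard and odds ratios are marginal. They lie closer to 1 than the ratios conditional on the factors. That is a different quantity, not a bias.

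A smaller point concerns interpretation. As written, the ITT and per-protocol Cox and logistic results differ in covariates as well as in subjects, so a discrepancy between them could not be put down to either one.

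**Working it through.** **Inputs from the documents.** N = 225; control screening 50% and intervention screening 65% by 6 months; HR stated as 1.5 (section 3.2). Two-sided alpha 0.05 (section 8.1.1). Random blocks of 2, 4, 6 or 8 within four strata (section 3.3). Follow-up to 12 months (section 8.2.1). Section 3.2 also assumes 6 months of accrual with at least 12 months of follow-up each.

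**Assumed, because the documents do not say.** Power of 80%; exponential times; 50% men; 40% aged 60 or over (25% as a check); and the hazard ratio for screening carried by each factor, called the factor HR below and varied from 1.0 to 2.0.

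**Step 1: the plan's own N.**
- HR = ln(0.35)/ln(0.50) = 1.515.
- Schoenfeld events = 4(1.960 + 0.842)²/(ln 1.515)² = 182.2.
- Probability of screening by 12 months: control 1 − 0.50² = 0.750; intervention 1 − 0.35² = 0.8775; mean 0.814.
- N = 182.2/0.814 = 224, or 225 if events are first rounded up to 183.

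Other readings at 80% power give 235 (HR 1.5, 12 months each), 209 (HR 1.515, section 3.2 accrual) and 219 (HR 1.5, section 3.2 accrual). At 85% power the range is 239 to 269, and at 90% it is 280 to 315. So 225 is consistent with an arm-only calculation at 80% power. It shows no more than that, since no power is stated.

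**Step 2: Cox power.** 10,000 simulated trials per row; arm HR 1.515; censoring at 12 months; baseline hazard solved so that overall control screening is 50% at 6 months; Wald tests.

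| Factor HR (each factor) | Arm only | Stratified | Adjusted | Adjusted minus arm only |
|---|---|---|---|---|
| 1.0 | 79.8% | 79.4% | 80.2% | 0.4 |
| 1.25 | 78.2% | 78.3% | 79.3% | 1.1 |
| 1.3 | 78.1% | 78.6% | 79.3% | 1.2 |
| 1.5 | 76.4% | 78.9% | 79.5% | 3.1 |
| 2.0 | 69.0% | 77.3% | 78.1% | 9.1 |

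The standard error of the paired differences is at most 0.33 points, so the 0.4 in the first row should be read as no difference. A factor HR of 1.5 means control screening at 6 months runs from 38% to 66% across strata. At 2.0 it runs from 30% to 76%, which is extreme.

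Sensitivity of the gain:
- Section 3.2 accrual and HR 1.5: 0.1, 1.7, 3.8 and 10.4 points at factor HR 1.0, 1.3, 1.5 and 2.0.
- 25% aged 60 or over: 0.0, 1.1, 3.2 and 9.1 points at the same values.
- Only one factor prognostic: 1.7 points at 1.5 and 5.3 at 2.0.

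**Step 3: Cox type I error** (Monte Carlo SE 0.2 points).

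| Factor HR | 1.0 | 1.25 | 1.3 | 1.5 | 2.0 |
|---|---|---|---|---|---|
| Arm only | 5.4% | 4.9% | 4.8% | 4.1% | 3.8% |
| Adjusted | 5.4% | 5.2% | 5.1% | 4.9% | 5.4% |

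A separately coded run with 3,000 replicates per cell and HR 1.5 gave Cox gains of about 0, 1, 3 and 11 points at factor HR 1.0, 1.25, 1.5 and 2.0. It also showed 6.2% adjusted type I error at 1.5 (SE about 0.4). Larger runs gave 4.9% (10,000 replicates) and 5.3% (16,000), so the 6.2% looks like simulation noise.

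**Step 4: logistic power, arm only / adjusted.**

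| Factor HR | 6 months | 12 months |
|---|---|---|
| 1.0 | 62.0 / 62.4% | 69.4 / 69.6% |
| 1.3 | 60.4 / 62.0% | 66.7 / 67.5% |
| 1.5 | 59.7 / 62.3% | 64.6 / 66.6% |
| 2.0 | 53.6 / 59.2% | 55.3 / 60.1% |

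**Step 5: marginal against conditional estimates at factor HR 1.5.** Cox HR 1.49 against 1.52; 6-month OR 1.83 against 1.89; 12-month OR 2.26 against 2.37.

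**The case against.** Nothing here is invalid. The arm-only tests hold their level, and a marginal effect is a defensible target when the question is whether clinics should adopt the tool. That stands, and it is why this is an efficiency point.

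The benefit rests on assumed prognostic strength. Section 1 speaks of US adults in general, whereas the trial enrols never-screened people aged 50 to 75 from one outreach list, with age split at 60. Neither factor may predict much in that group. This also stands: with weak factors the gain is 0 to 2 points, and the large figures need an extreme case.

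Adjustment is not wholly without cost. It assumes proportional hazards for the two factors. When their effects were made to reverse after month 6 (factor HR 1.5 and 2.0; 20,000 replicates under the null), adjusted type I error was 5.4% and 5.5% (SE 0.16), against 5.0% and 4.9% for the stratified model. The excess is real but small, about the size seen for the arm-only model at factor HR 1.0 in step 3. Adjusted power was still 1.6 and 5.3 points above arm-only.

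The per-protocol set is selected after randomisation on the availability of 12-month data (section 5). Balance is then no longer assured, which would be a reason to adjust there. The SAP does not give this reason, and it is no argument against adjusting the ITT models.

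Finally, the trial is open-label, so changing the primary model is harmless only if it is done before outcomes are examined by arm. That is right, and the fix includes it.

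**Conclusion.** The point holds as a recommended improvement, not a validity error. The ITT primary test and two ITT secondary tests omit the factors used to randomise, while the per-protocol versions include them. The cost in Cox power is about 0 to 2 points if each factor HR is at most 1.3, about 2 to 4 at 1.5, and 5 to 10 only at 2.0. For the logistic models the loss is 0.8 to 1.6 points at 1.3, 2.0 to 2.6 at 1.5, and 4.8 to 5.6 at 2.0.

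These sizes rest on the assumed factor strengths, stratum proportions and exponential times; the direction does not depend on the exact values. If 225 was set for 80% power, the plan has little to spare. If the factors turn out not to be prognostic, adjustment shows no measurable power loss.

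**What to change.** - **Section 8.2.2:** make the primary ITT analysis a Cox model with study arm, gender and age group (under 60; 60 and over). A Cox model stratified by the two factors is an acceptable alternative if proportional hazards for them is in doubt. Name one of the two in advance.
- **Section 8.3.2:** add the same two factors to the ITT logistic models at 6 and 12 months.
- **Estimand:** state that the reported hazard ratio and odds ratios are conditional on gender and age group, and report the arm-only models as supportive marginal estimates.
- **Consistency:** state that the ITT and per-protocol Cox and logistic models use the same covariates. Limit the statement to these models. The ITT screening-intent models, "which include study arm and account for time (pre-intervention/post-intervention) and with a random effect for subject", are not changed by this point.
- **Timing:** make the change before outcomes are examined by arm.

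The cost is SAP wording. Both variables are needed to randomise, so they are known for every ITT subject, and N, data collection and follow-up are unchanged. The adjusted model brings the proportional-hazards assumption discussed above. The stratified model avoids it, at a cost when neither factor is prognostic of 0.4 points against arm-only (79.8% to 79.4%) or 0.8 against the adjusted model (80.2% to 79.4%).
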